Credibility and Expectancy Questionnaire (CEQ)	PC/RA		x	x			
Pre-Treatment Health Interview (+ BL PTHA addendum)	IE	x					
Post-Treatment Health Interview (+ FU PTHA addendum)	IE			x	x	x	
Structured Diagnostic Interview for Headache –Revised (SDIH-R)	IE	x		x	x	x	
Ohio State University TBI Identification Method-Interview Form (OSU TBI-ID-SF)	IE	x					
Selection of Index Event for the CAPS-5	IE	x					
Clinician Administered PTSD Scale-5 (CAPS-5)	IE	x		x	x	x	
Self-Injurious Thoughts and Behaviors Interview –Short Form	IE	x		x	x	x	
Tinnitus Functional Index	IE	x		x	x	x	
PTSD Checklist List-5 (PCL-5)	PC/RA	x	x	x	x	x	x
Cognitive Emotions Regulations Questionnaire –Short (CERQ-Short)	PC/RA	x		x	x	x	
Posttraumatic Cognitions Inventory (PTCI)	PC/RA	x		x	x	x	
Response to Stressful Experiences Scale (RSES)	PC/RA	x					
Patient Health Questionnaire-15 (PHQ-15)	PC/RA	x		x	x	x	
Veterans Rand 12 Item Health Survey (VR-12)	PC/RA	x		x	x	x	
PROMIS Sexual Function	PC/RA	x		x	x	x	
Brief-Inventory of Psychosocial Functioning (B-IPF)	PC/RA	x		x	x	x	
Insomnia Severity Index (ISI)	PC/RA	x		x	x	x	
PROMIS Sleep-Related Impairment and Disturbance	PC/RA	x		x	x	x	

Assessments (cont.)	PC/RA or IE	BL	TX	Post	3MFU	6MFU	DC
Snoring, Tired, Observed, Blood Pressure (STOP)	PC/R A	X					
Community Reintegration of Injured Service Members (CRIS)	PC/R A	X		X	X	X	
NIH Cognition Battery (via computer)	PC/R A	X		X	X	X	
PTHA Study Missing Data Assessment	PC/R A						X
Online Forms:	1.) Daily Headache Diary 2.) Profile of Mood States 3.) Sleep Quality/Quantity 4.) Daily Stress Inventory						
					Participant will complete online entries twice daily. Entries will occur before, during, and after treatment for a total of 14 weeks.		

* DC = participant discontinued participation (i.e., drop out of treatment or follow-up)

6.1.3. Inclusion and Exclusion Criteria.

Inclusion Criteria:

- adult (ages 18 and above)
- U.S. military Veterans and active duty personnel with military service during a post-9/11 deployment
- have sustained a traumatic head injury.

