- Cognitive Processing Therapy-Cognitive Only (CPT-C). Cognitive Processing Therapy (CPT) is a trauma-focused treatment that involves learning to recognize and challenge thoughts related to traumatic brain injury. Participants assigned to this treatment arm will be asked to meet with a study therapist twice a week for

Randomized Clinical Trial of Cognitive-Behavior Therapy for Posttraumatic Headache

approximately 6-weeks for a total of 12 one-hour sessions. Each treatment will take place at the South Texas Veterans Healthcare System (Audie Murphy Hospital) or the UTHSCSA STRONG STAR clinic. During this treatment, participants will be asked to think about how they received their traumatic brain injury and their beliefs about the meaning of the event, as well as their current beliefs about themselves and others. Topics such as safety, trust, control, self-esteem, and intimacy will be discussed. Participants will be expected to complete assignments outside of session to practice skills learned in treatment.

- Treatment as Usual (TAU). Participants assigned into the Treatment as Usual (TAU) condition will receive treatment by their primary provider as indicated. The participants will meet with study staff twice during the treatment phase to complete assessments.

Assessments

- All participants regardless of treatment group will be asked to complete headache diary on-line twice a day.
- Blood will be drawn prior to treatment, during two of the treatment sessions, and at the 1- and 6-month assessments.
- Two weeks before the scheduled 1-, 3- and 6-month assessments, participants will once again be asked to complete headache diaries for two weeks prior to the evaluations.

All evaluations will be audio-recorded and CCBT and CPT-C therapy sessions will be audio-recorded to make sure that the study staff is correctly following the study procedures. These recordings will be reviewed by research experts who are part of the research team.

Assessment of Discontinued (i.e., treatment/assessment dropout) participants.

- All participants who discontinued participation in this study before completing study treatment and follow-up assessments will be contacted by phone by a project coordinator or research assistant and asked about their willingness to participate in a 10-15 assessment of their symptoms and reason for discontinuing participation. Participants will have the option to opt in to the assessment by giving verbal consent over the phone.

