Advanced Data Center (ADC) has 24x7 onsite security, card key, biometric access controls and video surveillance. University of Texas Health Science Center at San Antonio (UTHSCSA) ADC facility also maintains Gen 2 firewall devices to protect and prohibit any unauthorized access to UTHSCSA data. All UTHSCSA network devices are monitored by state of the art monitoring applications that include configuration audit, management, and availability 24x7.

Statistical Consideration

6.3.1 Sample Size Estimation.

This study will consent approximately 438 study participants with the goal of having 192 participants randomized for analysis.

6.3.2 Primary (i.e., primary outcome variables) and secondary endpoints.

The primary outcomes are headache symptoms and PTSD symptoms.

6.3.3 Data analysis.

Treatment groups will be compared on baseline variables. Dropout during treatment resulting in lack of outcome data can bias analyses. If attrition can be successfully modeled with logistic regression on the basis of baseline characteristics, and particularly if there is evidence of differential attrition, strategies such as inverse probability weighting can supplement the outcome analyses. Assuming that headache disability data (HIT-6; our primary outcome for this research) is reasonably normally distributed across the sample, treatment effects of the clinical interventions (CCBT and CPT-C) over the Treatment as Usual- Control condition will be analyzed using a general linear mixed (GLM) model with baseline scores used as a covariate. Unlike ANOVA, mixed effects models permit heterogeneity of variance in the treatment groups. If HIT-6 data are non-normal, a generalized linear model will be used (e.g., Poisson regression).

Two joint primary comparisons will be conducted comparing both active treatments to TAU. To adjust the alpha level for these joint hypotheses, we will interpret both at the alpha = 0.025 significance level. Secondary analyses will examine differences between the two active interventions as well as sensitivity analyses of the primary outcomes considering missing data, adherence to the protocol, or imbalances between the groups at baseline. Additional analyses will consider the secondary outcomes and differences between the groups at other time points.

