Randomized Clinical Trial of Cognitive-Behavior Therapy for Posttraumatic Headache

higher the subscale score, the more a specific cognitive strategy is used. Psychometric testing of the 36-item CERQ was conducted using a group of 547 secondary school students aged 12 to 16 attending a state school in the Netherlands. Internal consistency of the subscales ranged from 0.71 to 0.92. The CERQ was positively correlated with both depression and anxiety as assessed with the subscales of the Symptom Check List-90. Test-retest

reliability for each of the subscales at five months ranged from 0.41 to 0.59. The CERQ-short form (Garnefski & Kraaij, 2006) is an 18-item questionnaire that produces the same 9 subscales as the 36-item questionnaire. A study of 611 adults from a general practitioner's office practice in the Netherlands indicated that the internal consistency of the 2-item subscales remained acceptably high ($\alpha = 0.67$ to 0.81). In support of the validity of the CERQ-short, correlations with outcome measures were comparable to reported results with the original CERQ in that the Rumination, Self-Blame and Catastrophizing subscales were related to more depression and anxiety symptoms, while the Positive Reappraisal subscale was related to fewer symptoms (Garnefski & Kraaij, 2006).

5. **Demographics:** We will use a standard CAP form to gather relevant demographics including: age, gender, ethnicity, date of concussion/TBI, mechanism of concussion/TBI, number of past concussions/TBIs, relevant comorbid medical conditions (e.g., cognitive decline, musculoskeletal or neuropathic pain –especially presenting in the head or neck).
6. **Health Interview (Pre-Treatment) and Health Interview (Follow-Up) also, pre- and post- HI addendum:** The Health Interview includes items regarding general health, hospitalizations, current and past psychiatric medications, thoughts about wanting to harm others, utilization of mental health services, utilization of outpatient medical services, and caffeine and tobacco use. Additionally, the health interview will include a review of the participant's medical record to identify provider-assigned ICD-9 diagnostic codes for chronic and neuropathic pain.

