15. Headache Management Self-Efficacy Scale (HMSE): This is a 25-item assessment rated on a 7 point Likert-type scale measuring one's confidence at preventing headaches (French, Holyroyd, & Peinell, et al, 1999).

16. Headache Specific Locus of Control Scale (HSLC): The HSCL is a 33 item measures scored on a 5-point Likert-type scale to measure an individual's perceptions that headache problems and relief are determined by: individual behaviors, healthcare professionals, or chance factors (Martin, Holyroyd, & Penzien, 1990).
17. Clinician-Administered PTSD Scale for DSM-5 (CAPS-5) : The CAPS-5 is structured interview that assesses the DSM-5 criteria for PTSD (Weathers et al., 2013). Each item is rated on a severity scale ranging from 0 (Absent) to 4 (Extreme/incapacitating) and combines information about frequency and intensity for each of the 20 symptoms. Additional items that are not included in the total score evaluate overall symptom duration, distress, impairment, dissociative symptoms, and global ratings by the interviewer. Validation studies are nearly complete to establish the psychometric properties of the CAPS-5 and findings will be reported in peer-reviewed publications. This interview is very similar to its predecessor, the CAPS for DSM-IV, which has been considered the gold standard for evaluating PTSD and demonstrated good reliability and validity (Weathers, Keane, & Davidson, 2001). In addition to reflecting diagnostic changes for PTSD in DSM-5, the CAPS-5 differs from the CAPS in that frequency and intensity ratings for each symptom are no longer scored separately, so the severity rating for each item determines whether a symptom is present or not. Subscale scores are calculated by summing severity scores for items in the following PTSD symptom clusters: re-experiencing, avoidance, negative alterations in cognitions and mood, and hyperarousal.
18. PTSD Checklist –DSM-5 (PCL-5): The PCL-5 (Weathers, et al., 2010) is a 20-item self-report measure update of the PCL designed to assess PTSD symptoms as defined by the DSM-5. The PCL-5 is currently available and has been shown to have good psychometric properties.
19. Neurobehavioral Symptom Inventory (NSI): The NSI is a 21-item assessment of post-concussive symptoms with a 3- factor structure (somatic/sensory, affective, and cognitive) (Caplan et. al, 2010).

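### The independent evaluator role gives both the follow-up Health Interview, which asks about mental health service use, and the CAPS-5, and no evaluator blinding is stated

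*Combined protocol and SAP*

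**What the plan says.** The assessment table in section 6.1.2 lists "Post-Treatment Health Interview (+ FU PTHA addendum" under the IE, marked at Post, 3 months and 6 months. The CAPS-5 is also under the IE, at baseline and the same three follow-up visits. The HIT-6 and PCL-5 are under PC/RA.

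Description of Study Measures, item 6, gives the content of the Health Interview, which includes "utilization of mental health services, utilization of outpatient medical services, and caffeine and tobacco use". It adds that "the health interview will include a review of the participant's medical record", for the purpose of finding pain diagnosis codes. Item 17 describes the CAPS-5 scoring: "Each item is rated on a severity scale ranging from 0 (Absent) to 4 (Extreme/incapacitating", with 20 symptoms and some global interviewer ratings.

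Section 6.2 sets out the arms. CPT-C runs for "approximately 6-weeks for a total of 12 one-hour sessions", CCBT has 8 sessions over a similar period, and TAU participants are treated by their usual provider and meet study staff twice for assessments.

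On outcomes, section 6.3.2 says "The primary outcomes are headache symptoms and PTSD symptoms" and names no instrument. Section 6.3.3 names one: "HIT-6; our primary outcome for this research".

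Item 8 uses the term Independent Evaluator without defining it. No section says that evaluators are blind to arm, that different people give the two interviews, in what order they are given, or that participants are asked not to mention their treatment. Section 6.2 has all evaluations audio-recorded, but as a check that staff follow procedures.

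**The concern.** In a psychotherapy trial the participant knows the arm, so an interviewer-rated outcome depends on the rater not knowing it. Here the schedule has the rating role ask, at every follow-up, a question whose honest answer is likely to differ by arm. Someone who has just finished 8 or 12 therapy sessions would naturally report them as mental health care.

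Each CAPS-5 item combines frequency and intensity into one judged severity score, so a rater who knows the arm has room to be influenced. If ratings drift lower for participants known to have had therapy, part of the apparent difference from TAU is rater expectation. The CAPS-5 is the only clinician-rated PTSD severity measure in the battery, so this would matter to any PTSD claim that rests on it.

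**Working it through.** **Step 1. Set the entries side by side.**

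| Measure | Given by | Follow-up visits | Bearing on this point |
|---|---|---|---|
| Follow-up Health Interview | IE | Post, 3, 6 months | asks about mental health service use |
| CAPS-5 | IE | Post, 3, 6 months | 20 items, each rated 0–4 by the interviewer |
| PCL-5 | PC/RA | Post, 3, 6 months | self-report |
| HIT-6 | PC/RA | Post, 3, 6 months | the measure named as primary in 6.3.3 |

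The arm-revealing question and the rated outcome fall to one role at all three visits. The HIT-6 and PCL-5 do not pass through that role.

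**Step 2. What the answer would show.** Study therapy is 12 sessions (CPT-C), 8 (CCBT) or none (TAU). TAU participants may receive mental health care from their own providers. Section 6.1.3 excludes only those currently in CPT or prolonged exposure. The answer is therefore an informative marker of arm, but not a certain one.

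**Step 3. How much a rating shift would matter.** The plan gives no figure to reproduce, so this is an illustration.

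Inputs:
- n = 64 per arm, alpha = 0.025 per comparison and r = 0.5 with baseline, from sections 6.3.3 and its power paragraph, where they are stated for the HIT-6. Applying them to the CAPS-5 is an assumption, as is a two-sided test (critical value 2.241).
- CAPS-5 SD of 10 to 14: assumed.
- Average shift of 1 or 2 points in favour of an active arm, with no true effect: assumed. Over 20 items this is 1/20 = 0.05 or 2/20 = 0.1 point per item.

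Formulas:
- SE = SD × √(1 − 0.5²) × √(2/64) = SD × 0.8660 × 0.1768 = SD × 0.1531
- False-positive rate = Φ(shift/SE − 2.241) + Φ(−shift/SE − 2.241)

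| SD | SE | Shift | Shift/SE | False-positive rate |
|---|---|---|---|---|
| 14 | 2.143 | 1 | 0.467 | 0.041 |
| 10 | 1.531 | 1 | 0.653 | 0.058 |
| 14 | 2.143 | 2 | 0.933 | 0.096 |
| 10 | 1.531 | 2 | 1.306 | 0.175 |

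With no shift the rate is 0.025. The shift is an average over the whole arm, so it mixes how often the rater learns the arm with how far the rating then moves. Two points in half of the ratings is 0.5 × 2 = 1 point on average.

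**Step 4. Does order alone protect the rating?** If the Health Interview always followed a locked CAPS-5, the Post rating would be protected. An IE who learned the arm at Post could still rate the same participant at 3 and 6 months.

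**The case against.** The best reply is that the documents do not establish several links in the chain.

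- **A reader might infer that a named primary outcome is biased.** Section 6.3.2 names only a domain. The PCL-5 fits it as well as the CAPS-5, and the power calculation rests on the HIT-6. This stands: the threat to a primary result depends on which PTSD measure is used.
- **A reader might infer that the schedule defeats a blinding safeguard.** The plan states no evaluator blinding, and independent may mean only that the evaluator is not the therapist. This stands. It does not clear the plan: if IEs are meant to be blind, the form works against it, and if they are not, the CAPS-5 is exposed anyway.
- **A reader might infer that the Health Interview comes just before the CAPS-5.** Row order in a schedule is not administration order, and a role is not necessarily one individual. This stands, but nothing in the plan prevents that sequence or separates the people.
- **Disclosure is inferred.** The form itself is not in the document and might exclude study sessions, and TAU participants may also report mental health care. This supports often rather than always.
- **Bias need not be beyond repair.** Recordings would allow masked re-rating where the recording does not itself reveal the arm, and the PCL-5 offers a comparison free of rater judgement. Both are fair, but the plan provides for no such re-rating.
- **The interview may sit with the IE for a reason**, since it asks about thoughts of harming others. The PC/RA already gives sensitive measures such as the PHQ-9 and the DSI-SS, so this is not a strong bar to moving it.

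**Conclusion.** The concern holds in a limited form. As scheduled, the role that rates the CAPS-5 also asks about mental health service use at every follow-up, and the plan states neither evaluator blinding nor any separation of the two. The CAPS-5 is therefore open to rater bias, and with it the primary PTSD domain if the CAPS-5 is the measure chosen for it. The HIT-6 and PCL-5 are not affected by this route, so the point does not call the HIT-6 comparison into question.

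The size and direction of any bias are not known. Bias favouring the therapies is the usual worry, not something the documents show. The rates of 0.041–0.058 and 0.096–0.175 show only that small average shifts would matter at this sample size. They rest wholly on the assumed shifts and SDs, and on alpha and r borrowed from the HIT-6 plan.

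**What to change.** In the section 6.1.2 table, move the Post-Treatment Health Interview and its addendum, including the record review, from the IE to the PC/RA. In section 6.2, state that IEs are blind to arm, that participants are asked not to tell the IE about their treatment, and that the IE records any unblinding at each visit. The blinding statement alone would not be enough, because the form would still ask the question.

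If the form must stay with the IE, give it only after the CAPS-5 is scored and locked, and use a different IE at later visits where existing staffing allows, because knowledge gained at Post carries over.

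The cost is slightly more PC/RA time and a short protocol edit. No new instrument or visit is needed.

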6. RESEARCH PLAN

6.1 Selection of Subjects

6.1.1. Subject Population. Potential participants will be recruited from the STVHCS Polytrauma Rehabilitation Center (PRC), military medical treatment facilities, and from the local community. Recruitment will target veterans and active duty personnel having returned from a post-9/11 deployment with chronic PTHA and symptoms of posttraumatic stress.

6.1.2. Source of Research Material. Please find a description of these measures at the end of this protocol. Assessments will be administered in person whenever possible. However, in order to accommodate participant schedules and/or instances in which a participant may have left the local area at the time of a follow up assessment, we may collect full or partial assessments in person or via phone or electronic data capture using a secure link to the encrypted STRONG STAR database. Assessments completed via phone or remote electronic data capture will not include biospecimen collection. Reasonable efforts will be made to collect all data as described in this protocol, but we expect some participants may not be able to complete part or all of any given follow up assessment.

Randomized Clinical Trial of Cognitive-Behavior Therapy for Posttraumatic Headache

Assessments	PC/RA or IE	BL	TX	Post	3MFU	6MFU	DC
Demographics and Military Questionnaire	PC/RA	x					
History of Head Injuries and History of Head Injuries Addendum	PC/RA	x		x	x	x	
Deployment Risk and Resiliency Inventory_2_Deployment Environment (DRRI_2_D)	PC/RA	x					
Deployment Risk and Resiliency Inventory_2_Postbattle Experiences (DRRI_2_P)	PC/RA	x					
Deployment Risk and Resiliency Inventory_2_Combat Experiences (DRRI_2_C)	PC/RA	x					
Life Events Checklist-5 (LEC-5)	PC/RA	x		x	x	x	
Patient Health Questionnaire-9 (PHQ-9)	PC/RA	x	x	x	x	x	
Depressive Symptom Index –Suicide Subscale (DSI-SS)	PC/RA	x		x	x	x	
Generalized Anxiety Disorder-7 (GAD-7)	PC/RA	x		x	x	x	
Alcohol Use Disorders Identification Test –Self Report (AUDIT)	PC/RA	x					
Quick Drinking Screen (QDS)	PC/RA	x		x	x	x	
Fagerstrom Test for Nicotine Dependence (FTND)	Self-report	x		x	x	x	
Fagerstrom Test for Nicotine Dependence-Smokeless Tobacco (FTND-ST)	Self-report	x		x	x	x	
Headache Management Self-efficacy Scale (HMSE)	PC/RA	x		x	x	x	
Headache-Specific Locus of Control Scale (HSLC)	PC/RA	x		x	x	x	
Headache Impact Test (HIT-6)	PC/RA	x		x	x	x	x
Neurobehavioral Symptom Inventory (NSI)	PC/RA	x		x	x	x	

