8.0 ADVERSE EVENTS, UNANTICIPATED PROBLEMS, AND DEVIATIONS

The IRB policy on reporting adverse events, unanticipated problems, and protocol deviations will be followed.

9.1 WITHDRAWAL FROM STUDY PARTICIPATION.

Participants may be withdrawn from the study if:

- The researcher believes that it is not in their best interest to stay in the study.
- The participant becomes ineligible to participate.
- The participant's condition changes and they need treatment that is not allowed while taking part in the study.
- The participant does not follow instructions from the researchers.
- The study is stopped.

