7. **Generalized Anxiety Disorder Screener (GAD-7):** The GAD-7 (Spitzer, Kroenke, Williams, & Lowe, 2006) will be used to assess generalized anxiety symptomology. This is a 7-item measure that asks participants to rate the frequency with which they have been bothered by anxiety symptoms within the past two weeks on a scale ranging from 0 ("not at all") to 3 ("nearly every day"). Scores on all items are summed to obtain a total severity score. Scores reflect no significant anxiety symptoms (0-4), mild anxiety symptoms (5-9), moderate anxiety symptoms (10-14), and severe anxiety symptoms (>15). Respondents also indicate the degree to which their anxious symptoms have made it difficult for them to do their work, take care of things at home, or get along with other people, from "not difficult at all" to "extremely difficult." The GAD-7 has been shown to have high internal consistency (e.g., $\alpha = .89$; Lowe et al., 2008) and has been shown to reliably discriminate between anxious and non-anxious diagnostic groups (Kroenke, Spitzer, Williams, & Lowe, 2010).
8. **Self-Injurious Thoughts and Behaviors Interview (SITBI):** The Self-Injurious Thoughts and Behaviors Interview (SITBI; Nock, Holmberg, Photos, & Michel, 2007) is a structured interview assessing the presence, frequency, and characteristics of self-injurious and suicidal thoughts and behaviors. The SITBI will be administered by an Independent Evaluator, who will instruct the participants to answer the questions based on their entire lifetime of experience. The SITBI has shown high interrater reliability, test-retest reliability, and concurrent validity (Nock et al., 2007).

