23. Depressive Symptom Index – Suicidality Subscale (DSI-SS): The DSI-SS (Metalsky & Joiner, 1997) will be used to assess current suicidal ideation. The DSI-SS is a 4-item self-report measure of suicidal ideation that focuses on ideation, plans, perceived control over ideation, and impulses for suicide. It is being used as a core measure in the Military Suicide Research Consortium. Scores on each item range from 0 to 3, with higher scores reflecting greater severity of suicidal ideation. Instructions will instruct the participants to respond based on the past week. A systematic review of measures of suicidal ideation and behaviors found that the DSI-SS had evidence of excellent internal consistency and concurrent validity (Batterham et al., 2014).
24. NIH Toolbox Cognition Battery: The NIH Toolbox is a recently developed comprehensive assessment tool with an emphasis on measuring outcomes in longitudinal epidemiologic studies and prevention or intervention trials across a lifespan (Akshoomoff, et al., 2014). The cognition battery is a brief and efficient computer-based neuropsychological test of the seven key cognitive domains: Executive Functioning, Episodic Memory, Working Memory, Processing Speed, Language, Attention and Reading. The oral reading subtest will not be administered to reduce subject burden. The battery requires only 20-30 minutes to administer.

25. Alcohol Use Disorders Identification Test (AUDIT) self-report version: The AUDIT (Babor et al., 2001) will be used to identify people with hazardous or harmful patterns of alcohol consumption and to index the severity of these problems. It will be administered as a self-report form. The AUDIT is a 10-item screening measure, developed by the World Health Organization (WHO), with three subscales (alcohol consumption, drinking behavior, and alcohol-related problems) that are scored on a 4-point scale for a highest possible total score of 40. The AUDIT has good internal consistency ($\alpha = .80-.93$) as well as sensitivity and specificity (Saunders, Aasland, Babor, De La Fuente & Grant, 1993; see Reinert & Allen, 2007, for review).

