26. Quick Drinking Screen (QDS) self-report version: The QDS (Sobell et al., 2003) will be used to measure alcohol consumption. It consists of 4 items probing frequency and quantity of alcohol consumption. It will be administered in a self-report form. The QDS has been validated against the Timeline Followback daily estimation measure of alcohol use, and it shows good psychometric properties (Roy et al., 2008; Sobell et al., 2003). The QDS's time-frame will be modified to match the "last two weeks" probed by the mandated depression and anxiety instruments for CAP studies (PHQ-9 and GAD-7). Like these other measures, the QDS can be administered frequently throughout CAP trials to track changes in alcohol use.
27. Brief Inventory of Psychosocial Functioning (B-IPF): This is a 7-item self-report instrument measuring respondents' level of functioning in seven life domains: romantic relationship, relationship with children, family relationships, friendships and socializing, work, training and education, and activities of daily living (Marx, 2013). Respondents indicate the degree to which they had trouble in the last 30 days in each area on a 7-point scale ranging from "0 = Not at all" to "6 = Very much." The B-IPF has demonstrated concurrent validity, and the full 80-item IPF from which it was created has strong test-retest reliability and internal consistency (Marx, 2013).
28. Patient Health Questionnaire – 15 (PHQ-15): The PHQ-15 (Kroenke, Spitzer, & Williams, 2002) is an abbreviated version of the original PHQ that asks about somatic symptoms and symptom clusters that account for more than 90% of physical complaints reported in an outpatient setting. The 15-item measure asks patients to report symptom severity on a scale ranging from 0 ("not bothered at all") to 2 ("bothered a lot"). The PHQ-15 has been found to have excellent internal reliability ($\alpha = .80$) and good convergent validity with scales such as the SF-12 and other measures of symptom severity and functionality (Kroenke, Spitzer, & Williams, 2002).

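### The self-injury interview is repeated at three follow-ups with only a lifetime recall window, so its presence items cannot show resolution, or recurrence in participants with a history at baseline

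*Combined protocol and SAP*

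**What the plan says.** The assessment table in section 6.1.2 lists the "Self-Injurious Thoughts and Behaviors Interview –Short Form" for administration by the independent evaluator. It is marked at baseline, Post, 3-month and 6-month follow-up, and not in the treatment or discontinuation columns. Item 8 of the Description of Study Measures calls it a "structured interview assessing the presence, frequency, and characteristics of self-injurious and suicidal thoughts and behaviors" and says it is given by an evaluator "who will instruct the participants to answer the questions based on their entire lifetime of experience". No other window for this interview, at follow-up or at any other visit, appears in the protocol.

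The Depressive Symptom Index suicidality subscale (DSI-SS, item 23) is marked at the same four visits. It "focuses on ideation, plans, perceived control over ideation, and impulses for suicide", and on recall the protocol says: "Instructions will instruct the participants to respond based on the past week".

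On safety events, section 8.0 says: "The IRB policy on reporting adverse events, unanticipated problems, and protocol deviations will be followed". Section 6.3.2 names headache and PTSD symptoms as the primary outcomes, and section 6.3.3 describes no analysis of the SITBI.

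**The concern.** An interview repeated three times after baseline is presumably meant to show what has happened since. A lifetime question is poorly suited to that, because its answer accumulates and never resets. The participants for whom it is least informative are those who already have a history of suicidal thoughts or self-injury. Section 6.1.3 does not keep them out: it excludes a psychiatric hospitalization in the previous six months and a current problem needing immediate treatment, but not a lifetime history.

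What is at stake is the description of safety by arm. Section 7.2 warns that treatment may temporarily worsen existing psychiatric symptoms. The SITBI is the only scheduled measure described as asking every arm about suicidal and self-injurious behaviour.

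**Working it through.** The plan states no figure on this point, so the check sets the schedule beside the measure descriptions.

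**1. What a lifetime presence item can show.** Inputs are the visit marks in the section 6.1.2 table and the recall rule in item 8, taken to apply at every visit.

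| Status at baseline | What happens before the follow-up | Lifetime item at follow-up | Item asking since last assessment |
|---|---|---|---|
| No history | Nothing | no (unchanged) | no |
| No history | First-ever event | no to yes | yes |
| History | Nothing further | yes (unchanged) | no |
| History | Recurrence | yes (unchanged) | yes |

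The last two rows give the same lifetime answer, so the item cannot separate them. A change from 'yes' to 'no' would be a reporting error, not resolution. The second row shows that first-ever events remain visible.

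**2. What frequency can add.** Item 8 says the interview also records frequency and characteristics. If frequency is a lifetime count F, new events could be derived as F(follow-up) minus F(baseline). That difference carries the recall error of both totals, and the protocol specifies no such derivation.

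**3. Whether another scheduled measure fills the gap.**
- DSI-SS (item 23): one week of recall; its listed content does not include behaviour or self-injury.
- Health Interview (item 6): hospital stays, use of mental health care and thoughts of harming other people. It could pick up a hospitalized event indirectly.
- PHQ-9 (item 20): described as a measure of depressive symptom severity.
- Discontinuation call (section 6.2): HIT-6, PCL-5, global change, views of the study and reasons for leaving.
- Adverse events (section 8.0): a general route under IRB policy, with no suicidality-specific ascertainment described.

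**4. How other instruments are handled.** Recall periods are written down elsewhere. DSI-SS has its week, and the Quick Drinking Screen (item 26) has its "time-frame will be modified to match the" two weeks of the depression and anxiety scales. Separate pre- and post-treatment Health Interviews are listed. Some history instruments (DRRI-2, OSU TBI-ID) are given at baseline only, although the Life Events Checklist and the head-injury history are repeated, so this pattern is not uniform.

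**5. Illustration of size.** The share of participants with a lifetime history is not in the documents. Assuming 10% to 50% of the 192 to be randomized:
- 192 × 0.10 = 19.2, about 19 participants
- 192 × 0.50 = 96 participants
- per arm of 64: 64 × 0.10 = 6.4 to 64 × 0.50 = 32

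Those participants could show no change on a lifetime presence item, whatever happened to them during the trial.

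**The case against.** The best reply is that item 8 is a three-sentence summary, not the interview script. It does not say that the lifetime instruction applies at every visit. The table names a short form whose items are not reproduced, and the follow-up version may already ask for recent counts or dates. That stands as a limit on certainty. It does not remove the point, because the follow-up window would then be unstated and would still need to be written down.

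A reader might go further and infer that the interview cannot show new events, or cannot compare arms on events after randomisation. The documents do not support either reading. First-ever events show as 'no' to 'yes' and can be counted by arm, and frequency and characteristics are also recorded.

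A reader might also try to size the gap as the part of the 3- to 6-month interval lying outside the DSI-SS week. That is not a valid measure. For behaviour, DSI-SS covers none of the interval. For ideation, it is a repeated current-state measure that was never meant to cover the whole of it.

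It is also fair to say that the adverse-event route could pick up an attempt or serious self-injury in any arm, that section 7.2 does not mention suicidal behaviour, and that no planned SITBI analysis is invalidated. These points keep the matter small. They do not give the interview a usable follow-up window for participants with a history.

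**Conclusion.** The point holds in a limited form. Three of the four scheduled administrations are governed by a recall rule that, followed as written, stops the presence items from showing resolution, or recurrence in participants with a history at baseline. Recurrences could be recovered only by subtracting recalled lifetime frequencies. Self-injurious or suicidal behaviour between visits is therefore poorly captured by the scheduled measures in that group.

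This assumes that the lifetime instruction is used at all visits and that the short form has no separate recent-period items; neither can be checked from the documents. The number of participants concerned depends on an unknown baseline rate.

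The effect is on safety description only. The HIT-6 primary comparisons and their power are unaffected. This is a cheap improvement, not a flaw in the main inference.

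**What to change.** In item 8, keep the lifetime window at baseline. For Post, 3-month and 6-month follow-up, instruct the evaluator to ask about the period since the last completed assessment, covering presence, frequency and the date of the most recent event. The date matters most at Post: section 6.1.6 places randomisation after the baseline assessment, so that window includes some time before it.

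Add a line to section 6.3.3 that post-randomisation self-injury and suicidal behaviour will be reported descriptively by arm. For follow-ups already done, state how new events will be derived from the frequency and characteristics items. If the follow-up form already uses a recent window, one clarifying sentence in item 8 is enough, plus the reporting line.

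The cost is a sentence or two of text and a changed lead-in on the follow-up form, with no new visit, instrument or staff. The small downside is that follow-up data collected before and after the change would not be fully comparable, so the report should say which window applied. The change does not reach participants who discontinue, since the interview is not part of their assessment.
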